10.2.1.6. Hematological Adverse Events

Hematological AEs will belong to the following 4 categories: neutropenia, febrile neutropenia, anemia, thrombocytopenia. The 4 categories include the following PTs:

- PTs used to identify neutropenia: neutropenia and neutrophil count decreased
- PTs used to identify anemia: anemia and red blood cell count decreased
- PTs used to identify thrombocytopenia: platelet count decreased and thrombocytopenia
- PT used to identify febrile neutropenia: febrile neutropenia

10.2.1.7. Ranking of Safety Outcome

The following order (from best to worst) will be used to rank safety outcomes:

- Recovered/resolved
- Recovered/resolved with sequelae
- Recovering/resolving
- Not recovered/not resolved.
- Unknown
- Fatal

10.2.1.8. Ranking of Action Taken With Tafasitamab

The following order (from best to worst) will be used to rank actions taken with tafasitamab:

- Dose not changed
- Drug administration delayed
- Infusion interrupted
- Infusion rate reduced
- Drug skipped
- Drug permanently discontinued

10.2.1.9. Ranking of Action Taken With Lenalidomide

The following order (from best to worst) will be used to rank actions taken with LEN:

- Dose not changed
- Dose reduced
- Drug administration delayed
- Drug skipped
- Drug permanently discontinued

10.2.2. Adverse Events of Special Interest

Information regarding AESIs that occur while on treatment will provided directly from the eCRF. The following are considered AESIs for this study:

- TLS
- IRRs and allergic reactions to study treatment ≥ Grade 3
- CRS
- Second primary malignancies
- Hepatitis B reactivation
- Progressive multifocal leukoencephalopathy
- Tumor flare reaction

10.2.3. Death

Information regarding the death date and reason will be captured in the "Death" eCRF.

Pretreatment death is defined as any death that occurs after the ICF is signed and before the first dose of study treatment.

On-treatment death is defined as any death that occurs after the first dose of study treatment and before the last dose of study treatment/EOT.

Post-treatment death is defined as any death that occurs after the last dose of study treatment/EOT.

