### 8.2 Discontinuation of Study Treatment

Study treatment must be discontinued for a patient under the following circumstances:

- Pregnancy or expressed intent to become pregnant
- Disease progression
- Withdrawal of consent
- Use of prohibited treatment, including participation in another interventional study and/or initiation of new anti-cancer treatment (see [Section 7.9](#) for details)
- Unacceptable toxicity or TEAE, as determined by the investigator
- Protocol Deviation that may impact the benefit/risk assessment for the individual patient following discussion with the Medical Monitor
- Occurrence of new diseases that could influence the treatment efficacy, for which the study medications are contraindicated or that are treated with a medication that is not permitted as a concomitant medication
- Any other medical condition that may jeopardize the patient's safety if he or she continues on study treatment

The investigator is encouraged to keep a patient experiencing clinical benefit on study treatment per investigator discretion unless significant toxicity puts the patient at risk or repeated cases of routine noncompliance put the study outcomes at risk.

An End of Treatment visit must be performed within 14 days after decision on treatment discontinuation. See the SoA ([Section 2](#)) for data to be collected at the time of treatment discontinuation and follow-up and for any further evaluations that need to be completed.

Patients who are withdrawn for any reason may not re-enter this clinical study at any time.

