### 12.3 Appendix 3: Study Specific Definitions

For the purposes of this protocol, **primary refractory disease** is defined as a disease progressing in the course of the first line treatment as per International Working Group response criteria (Cheson *et al.*, 2007), and/or, showing a response of less than a PR to first-line treatment or disease recurrence/progression within  $\leq 6$  months from the completion of first-line therapy.

**Disease refractory to last treatment** is defined as having had less than a PR to the most recently administered systemic therapy.

**Relapsed/progressive/recurrent disease** reflects the appearance of any new lesions or increase by  $\geq 50\%$  of previously involved sites from nadir according to the International Working Group response criteria (Cheson *et al.*, 2007), after the most recent systemic therapy.

**First act of recruitment (EU):** For purposes of EU clinical trial regulation (536/2014) the first act of recruitment of a potential patient is defined as the date of initiation of the first site.

**Start of study:** A patient is considered to have started the study and entered the screening period when they have signed the informed consent form.

**End of Treatment:** The end of treatment is defined as the date when the patient has received last tafasitamab dose. An end of treatment visit will be performed within 14 days after decision on treatment discontinuation.

**End of Study:** The end of the study is reached when all patients still on study treatment have been followed for at least 3 years, or when the final patient on study has completed their last visit, whichever comes first.

Patients who are receiving ongoing treatment at the end of study may continue treatment with either of the options below upon assessment of a clinical benefit of continued treatment by the investigator and in accordance with the local regulatory guidance:

- commercially available tafasitamab for the approved dose regimen locally; or
- participation in the tafasitamab extension study if above option is not available

**End of study visit for a patient:** An end of study visit for a patient is defined as when the patient has completed 90 day safety follow up after the last tafasitamab dose given.

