4.1.9. Handling of Missing and Incomplete Dates

In general, values for missing dates will not be handled unless methods for handling missing dates are specified in this section or relevant sections. The original reported dates collected in the eCRF should be used in all relevant listings. The following rules will be used for handling partial dates for analyses requiring dates.

When the date of the last dose is used in deriving variables such as duration of treatment or TEAE flag, a missing or partial date of the last dose will be handled as follows:

- If only the day is missing, then the earlier date of the last day of the month or the date that the participant discontinued treatment will be used.
- If both the month and day are missing, then the earlier date of 31 DEC of the year or the date that the participant discontinued treatment will be used.
- Otherwise, the date that the participant discontinued treatment will be used as the date of the last dose.

For relevant efficacy endpoints, a partial date of the death date will be handled as follows in the calculation:

- If mmyyyy for the last known alive date = mmyyyy for the death date, then the death date will be set to the day after the last known alive date.
- If mmyyyy for the last known alive date < mmyyyy for the death date, then the death date will be set to the first day of the death month.
- Otherwise, the partial death date will not be imputed.

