4.2.3. Date of Last Administration of Study Drugs

The date of last administration of study drug ("last date of study drug") is the last date when a nonzero dose of study drug is administered. Last date of study drug is defined for each drug that is part of the study treatment. For tafasitamab, this date defines the EOT.

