4.2.5. Date of Last Administration of Study Treatment

The date of last administration of study treatment ("last date of study treatment") is the last date when a nonzero dose of any component of the study treatment is administered. For example, if the last dose of tafasitamab is taken on 13 APR 2022, and last dose of LEN is taken on 20 APR 2022, then the "last date of study treatment" is 20 APR 2022. In case of exposure to only 1 component of the study treatment, the date of last administration of study drug will be used.

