6.4.4.6. Compliance

6.4.4.6.1. Compliance With Tafasitamab

The compliance rate will be summarized and the number (%) of compliant and noncompliant participants will be reported by visit for the SAF, PAS, and FAS.

For visits in which no infusion was planned (eg, EOT), compliance will not be reported.

A listing of tafasitamab dose administration will be provided for the ENR with inclusion in the SAF, PAS, and FAS noted.

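### SAP 10.2.3 sets the on-treatment death cut-off before the last dose actually given, so with correct dates no death can be on-treatment and essentially every death is reported as post-treatment

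*SAP*

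**What the plan says.** SAP 10.2.3 sorts deaths into three timing classes. A pretreatment death falls between consent and the first dose. For the second class the text is: "On-treatment death is defined as any death that occurs after the first dose of study treatment and before the last dose of study treatment/EOT". For the third it is: "Post-treatment death is defined as any death that occurs after the last dose of study treatment/EOT".

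Both cut-offs are defined elsewhere as doses that were given:

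- SAP 4.2.5 takes the last date of study treatment as "the last date when a nonzero dose of any component of the study treatment is administered".
- SAP 4.2.3, on the last nonzero dose of a study drug, adds: "For tafasitamab, this date defines the EOT".
- Protocol Appendix 3 agrees: "The end of treatment is defined as the date when the patient has received last tafasitamab dose".

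The split is planned for the SAF and PAS (SAP 10.2.4.1.2) and the ENR (SAP 10.2.4.2.1), as Table 3.2.24.1.x in Appendix A. SAP 10.2.5 repeats it as an indicator in the death listing. By contrast, the TEAE window in SAP 10.2.1.3 runs to 90 days after the last dose.

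**The concern.** A class that requires death to precede the decedent's own last dose has no members unless a date is wrong. The neighbouring class is empty as well, because the SAF, PAS and ENR (SAP 5.3.5, 5.3.2 and 5.3.3) all require at least one dose. What remains is a single post-treatment row that mixes a death one day after an infusion with a death three months later.

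The trial's primary objective is safety and tolerability, and SAP section 3 itself lists death among the ways treatment ends. A reader who sees a zero in the on-treatment row could take it as a safety finding, when it follows from the wording. A fatal event starting the day after dosing would be treatment-emergent in the TEAE tables and a post-treatment death in this one.

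**Working it through.** The plan gives no figure here to reproduce, so the check is on the logic of the rule.

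**Step 1. The rule as an inequality.** Let d = date of death minus date of last dose, in days. Under SAP 10.2.3, after the first dose:

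- on-treatment requires d < 0;
- post-treatment requires d > 0;
- d = 0 meets neither, if only dates are compared. The Death eCRF is described as capturing a date and a reason.

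Doses are given to living patients, so true dates always give d ≥ 0. This holds whether the last dose is that of any component (SAP 4.2.5) or of tafasitamab (SAP 4.2.3, Protocol Appendix 3).

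**Step 2. Count over the 90-day follow-up.** For d = 0, 1, …, 90 there are 91 possible days: 0 on-treatment, 90 post-treatment (d = 1 to 90), and 1 in no category (d = 0). The d = 0 case is realistic, because LEN is taken daily on Days 1–21 (Protocol 7.1.2). These are counts of days, not probabilities of death.

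**Step 3. Enumeration.** Death days 0 to 399 after the first dose were crossed with every feasible last tafasitamab and last LEN date on a 7-day grid, none later than death.

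| Anchor | On | Post | No class | Total |
|---|---|---|---|---|
| Last dose of any component | 0 | 443,555 | 3,364 | 446,919 |
| Last tafasitamab dose | 0 | 445,208 | 1,711 | 446,919 |

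**Step 4. How a death could still enter the row.** When the day of the last dose is missing, SAP 4.1.9 says "the earlier date of the last day of the month or the date that the participant discontinued treatment will be used". Take a last dose recorded only as March 2024 and a death on 20 March (invented dates). The imputed last dose is min(31 March, discontinuation date):

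| Recorded discontinuation | Imputed last dose | d | Class |
|---|---|---|---|
| 15 March | 15 March | 20 − 15 = +5 | post-treatment |
| 20 March | 20 March | 20 − 20 = 0 | none |
| 25 March | 25 March | 20 − 25 = −5 | on-treatment |
| missing | 31 March | 20 − 31 = −11 | on-treatment |

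Over 32,304 combinations with the day missing, on-treatment deaths numbered 0 when the discontinuation date was before or on the day of death. They numbered 5,799 when it was five days after death or missing. If EOT were instead programmed as the eCRF discontinuation date, a date entered after the death would have the same effect without imputation. In both cases the patient enters the row because of how a date was recorded.

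**Step 5. The effect of a window.** If on-treatment becomes 0 ≤ d ≤ N, the 91 days split as follows:

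| N (illustrative) | On-treatment | Later, to day 90 |
|---|---|---|
| 0 | 1 | 90 |
| 28 | 29 | 62 |
| 30 | 31 | 60 |
| 90 | 91 | 0 |

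With N = 90, the post-treatment row would hold only days 91–97 (the ±7-day margin of the follow-up visit in Protocol Table 3) and late reports, because Protocol 5.1 provides no survival follow-up.

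**The case against.** The strongest reply is that EOT has other meanings. SAP 6.4.4.6.1 uses it for a visit: "For visits in which no infusion was planned (eg, EOT), compliance will not be reported". Protocol 8.2 schedules that visit: "An End of Treatment visit must be performed within 14 days after decision on treatment discontinuation". One could then treat a death with no earlier EOT visit as on-treatment and a death after the visit as post-treatment, which would be a usable split. But that is not what the SAP says. Its explicit definition of EOT is a dose date, and a patient who dies on treatment has no visit date to compare. The eCRF discontinuation date does no better: if it equals the death date, the strict wording still excludes the death.

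Some of the opposing case stands:

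- A reader might infer that the table must show zero on-treatment deaths whatever happens. The documents do not support that. Step 4 gives two artefact routes, and Table 3.2.24.1.x is marked as a standard table whose programming is not in the documents.
- Partial tafasitamab dates should be uncommon, since infusions are supervised and recorded (Protocol 7.7). SAP 4.1.9 gives treatment duration and the TEAE flag as examples of where its imputation applies, and does not name death timing.
- A reader might infer that the window must be shorter than 90 days. Nothing in the documents requires this; 90 days is the only post-dose safety window that the SAP states.
- The listing gives death dates beside tafasitamab and LEN start and end dates, so a careful reader can recover the timing of each death.

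**Conclusion.** The point holds. On the SAP's and protocol's own definitions, and with complete and correct dates, the on-treatment and pretreatment rows are empty in the SAF, PAS and ENR. Essentially every death is classed as post-treatment, and a death on the last-dose day has no class if dates alone are compared. The rule is wrong as written.

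Its reach is narrow: one timing split in Table 3.2.24.1.x and one listing flag. It would be wrong to infer that deaths are lost or that the primary endpoint is distorted. The breakdown by cause of death, the fatal-TEAE table and the listed dates are unaffected, and no primary or secondary endpoint uses the split. The documents give no expected number of deaths, so the number of patients affected cannot be estimated.

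The conclusion rests on reading EOT as SAP 4.2.3 and Protocol Appendix 3 define it.

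**What to change.** In SAP 10.2.3:

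1. Define on-treatment death as death on or after the first dose of any study drug and no later than a stated number of days after the last dose of any study drug (the SAP 4.2.5 date), including the last-dose day.
2. Define post-treatment death as any later death.
3. Remove `/EOT` from both definitions so that there is one anchor. The choice matters once a window exists, because Protocol 7.3.1.4 allows LEN to continue after tafasitamab has stopped.
4. The sponsor chooses the window and states how it relates to the 90-day TEAE window, noting that 90 days would leave few post-treatment deaths.
5. Report pretreatment deaths on the SPS, or drop that row from the SAF, PAS and ENR tables.

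The cost is SAP wording, the matching table shell and the listing flag. No new data are needed.

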10.2.4. Adverse Events Summaries

10.2.4.1. Summary of Treatment-Emergent Adverse Events and Deaths for the Safety Analysis Set and Primary Analysis Set

10.2.4.1.1. General Considerations

The primary safety analysis will be performed for the PAS, and a supplemental safety analysis will be performed for the SAF. The number (%) of participants who had any TEAE will be provided along with the TEAE incidence. Treatment-emergent AEs that occur after the start date of a prohibited concomitant medication will be excluded from the primary and supplemental safety analyses. No TEAE data will be collected after withdrawal of consent.

Treatment-emergent AEs will be classified into the following categories: seriousness, causality (suspected relationship to study treatment), toxicity (determined according to CTCAE v5), intensity, outcome, and action taken.

Specifically, all summaries of treatment-related TEAEs (causality) will be divided into the following 4 sections: related to any component of study treatment, related to tafasitamab only, related to LEN only, and related to both tafasitamab and LEN.

All summaries of TEAEs leading to treatment discontinuation will be divided into the following sections: discontinuation of tafasitamab, discontinuation of LEN, discontinuation of both tafasitamab and LEN.

The incidence of TEAEs will be summarized in incidence tables. If a participant experiences more than 1 occurrence of the same TEAE, the occurrence with the greatest intensity/toxicity, worst outcome, worst action taken, or the closest association with the study treatment will be counted in the summary tables.

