5.2. Treatment Groups

Data will be summarized overall and by treatment group

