6.2.3. Summary Statistics of Enrollment

Summary information regarding the enrollment of participants will be provided in order to describe the maturity of data and quality of follow-up for the safety and efficacy analyses. The following will be presented for the FAS and SAF:

- Duration of enrollment period (months) = (date of last participant enrolled date of first participant enrolled + 1) / 30.4375. This will be reported for overall only.
- Date of first participant enrolled.
- Date of last participant enrolled.

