7.3.4. Summary Statistics of Progression-Free Survival Follow-Up

Summary information regarding the follow-up of participants will be provided in order to describe the maturity of data and quality of follow-up for the efficacy analyses. The following will be presented for the FAS:

• Duration of follow-up time for PFS (months) = (date of event or censoring for PFS – study start reference date + 1) / 30.4375. Date of event or censoring is the same as defined in Section 7.3.2. This duration of follow-up will be estimated using a reverse Kaplan-Meier method to present the mean, 25th percentile, median, and 75th percentile. This will be reported based on the FAS, for the overall and recommended tafasitamab dose only.

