10.2.1.3. Treatment-Emergent Adverse Event

A TEAE is defined as any AE that starts or worsens after the first dose of study treatment until 90 days after the last dose of the study treatment. An AE that was present prior to study drug administration but increased in severity after treatment start will also be included as a TEAE.

Events with missing onset dates will be included as a TEAE if the end date is not before the first dose of study treatment.

If the start date and time of an AE are partially or completely missing, the AE will be assumed to be a TEAE if it cannot be proven that the AE did not occur or worsen during the treatment period (worst-case approach).

Any missing onset date of a TEAE will be handled according the following rules:

- If completely missing, then Day 1 will be used.
- If only the day is missing, then the first day of the month or Day 1, whichever is later, will be used.
- If both the month and day are missing, then 01 JAN of the year or Day 1, whichever is later, will be used.

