10.2.4.2. Summaries of Treatment-Emergent Adverse Events and Deaths for the Enrolled Population Set

10.2.4.2.1. Summaries

For the ENR, an overall summary of AEs by treatment group will include the same information described in Section 10.2.4.1.2.

For the ENR, the following summary tables showing the number (%) of participants will be provided by tafasitamab dose group and overall:

- TEAEs by SOC and PT
- TEAEs by SOC, PT, and CTCAE grade category
- Grade 3 or higher TEAEs by SOC and PT
- Serious TEAEs by SOC and PT
- Serious TEAEs by SOC, PT, and CTCAE grade category
- Grade 3 or higher serious TEAEs by SOC and PT
- TEAEs by SOC, PT, and initial intensity
- Treatment-emergent AESIs by SOC and PT
- Treatment-emergent AESIs by SOC, PT, and CTCAE grade category
- Grade 3 or higher treatment-emergent AESIs by SOC and PT

Deaths in the ENR will be summarized if they occur pretreatment, on treatment or post-treatment and if due to disease progression or an AE. An overall summary of deaths will be generated for the ENR. The number (%) of participants with events will be presented.

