10.2.5. Adverse Event and Death Listings

All AEs/TEAEs will be listed by cohort and treatment group and sorted by participant identification number along with the start date (day) and end date (day), duration, if serious, if an AESI, if related to tafasitamab/LEN, toxicity grade (highest), action taken with tafasitamab/LEN, other actions taken, tafasitamab start/end dates, LEN start/end dates, outcome, earliest date participant received prohibited concomitant medication (if applicable), and a flag to evaluate whether predefined safety event criteria are met. Listings will be generated for the ENR, with inclusion in the SAF and PAS noted, for the following:

- All AEs recorded throughout the study to show all information captured in the "Adverse Event" eCRF. The listing will include a flag to evaluate if the AE meets the predefined safety events criteria.
- All infusion-related AEs recorded throughout the study to show all information captured in the "Adverse Event" eCRF.
- All SAEs recorded throughout the study to show all information captured in the "Adverse Event" eCRF, including criteria for SAE met.
- All AESIs recorded throughout the study to show all information captured in the "Adverse Event" eCRF, including criteria for AESI met.
- All AEs with an onset date after the start date of prohibited concomitant medication.

All deaths, with an indicator if death occurred pretreatment, on treatment, or post-treatment, will be listed by cohort and treatment group and sorted by participant identification number along with the date of death (day) and cause of death, tafasitamab start/end dates, LEN start/end dates, and if applicable, earliest date participant received prohibited concomitant medication. The listing will be generated for the ENR, with inclusion in the SAF and PAS noted, and will include all assessments/events and a flag for those that are pre- and post-treatment assessments/events.

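### At the C3D28 primary completion analysis, crude TEAE percentages by dose group rest on follow-up that depends on entry date, and the visible SAP plans no common-window TEAE table and no TEAE follow-up by dose group

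*SAP*

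**What the plan says.** - **Timing.** SAP 3.5.2 places the primary completion analysis at the point when every participant has reached Cycle 3 Day 28 or stopped study treatment. Primary and secondary objectives are analysed then. No participant's data are truncated at C3D28.
- **TEAE window.** SAP 10.2.1.3 counts "any AE that starts or worsens after the first dose of study treatment until 90 days after the last dose of the study treatment".
- **Statistic.** SAP 10.2.4.1.1: "The incidence of TEAEs will be summarized in incidence tables". Protocol Table 17 gives the estimator as frequency and percentage. No person-time or time-to-event method for TEAE incidence is visible.
- **Breakdown.** SAP 5.2: "Data will be summarized overall and by treatment group". For the enrolled set, SAP 10.2.4.2.1 is explicit that tables "showing the number (%) of participants will be provided by tafasitamab dose group and overall".
- **Order of entry.** The Protocol synopsis describes two sequential cohorts, then an expansion at the recommended dose. The DSMC meets once at least 6 patients in each cohort have completed 35 days.
- **Follow-up displays.** SAP 6.2.3 sets out to "describe the maturity of data and quality of follow-up for the safety and efficacy analyses". It then gives the length of the enrolment period ("This will be reported for overall only") and the first and last enrolment dates, which carry no such limit. SAP 7.3.4 gives PFS follow-up "for the overall and recommended tafasitamab dose only". The 35-day predefined safety events appear in SAP 10.2.5 as a marker: "The listing will include a flag to evaluate if the AE meets the predefined safety events criteria".

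**The concern.** Dose is tied to calendar entry. A patient still on treatment at the cut contributes all the time since entry, so the dose that is not expanded is observed longer on average. A term that keeps accruing after Cycle 3 will then tend to show a higher percentage in that column even if the two doses carry the same risk.

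Setting a recommended dose is a primary objective with TEAEs as its endpoint (SAP Table 1), and this cut is the first planned full report on it. A descriptive reading across columns is foreseeable although no test is planned. For late-accruing terms such a reading would mix dose with follow-up, and no planned TEAE table takes the two apart.

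**Working it through.** The documents give no precision figure for TEAE incidence, so there is nothing to reproduce. The check asks how large the gap could be at equal true risk.

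**From the documents.** C3D28 = 3 × 28 = day 84. The TEAE tail is 90 days, about 51 patients enrol, and a month is 30.4375 days (SAP 4.3.3), so 84 days = 2.76 months and 90 days = 2.96 months.

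**Minimum entry gap.** Assume each cohort opens only after the previous cohort's 35-day review. The first 6 patients of Cohort 1 then enter at least 2 × 35 = 70 days before the first expansion patient. Their potential follow-up is at least 84 + 70 = 154 days, against 84 for the last patient.

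**Assumed, because the documents do not say.** Uniform entry over 6, 12 or 24 months; exponential treatment duration with median 4, 9 or 18 months; identical constant risk of 2% or 5% per month; 6 patients on the unexpanded dose and 45 on the other (inferred from a partly redacted sentence in Protocol 5.2); Cohort 2's or Cohort 1's dose expanded. That makes 3 × 3 × 2 × 2 = 36 settings.

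**Formula.** F is cut-off minus entry, a the tail, and λ and μ the monthly event and treatment-stopping rates. TEAE follow-up is W = min(treatment + a, F), and for F > a

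p = 1 − [ e^(−λa) · μ/(λ+μ) · (1 − e^(−(λ+μ)(F−a))) + e^(−μ(F−a) − λF) ].

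**Worked case.** 12-month enrolment, 9-month median (μ = ln 2 / 9 = 0.077), λ = 0.05, Cohort 2's dose expanded.

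- Expected entry of the i-th of 51 patients is 12i/52 months. The last enters at 11.77, so the cut is 11.77 + 2.76 = 14.53.
- Patients 1–6 (mean rank 3.5): mean F = 14.53 − 0.81 = 13.72. Patients 7–51 (mean rank 29): mean F = 14.53 − 6.69 = 7.84.
- At F = 13.72: p = 1 − [0.863 × 0.606 × 0.745 + 0.220] = 0.39. Averaging p over patients 7–51 gives 0.28.
- Simulation (20,000 replicates) agrees: 39% vs 28%, a gap of 11.0 points, with median TEAE follow-up 11.9 vs 6.3 months.

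**Results.**

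| Setting | Unexpanded minus expanded |
|---|---|
| All 36 constant-risk settings | 2.3 to 16.3 points (0.1 to 1.0 patient in 6) |
| Lowest (2%, 4-month median, 6-month enrolment, Cohort 1's dose expanded) | 11.5% vs 9.2% |
| Highest (5%, 18-month median, 24-month enrolment, Cohort 2's dose expanded) | 55.4% vs 39.2% |
| Front-loaded risk (Weibull shape 0.5), 18 settings | 2.1 to 8.9 points |
| Worked case, no 90-day tail for anyone | 8.8 points |
| Worked case, unexpanded group of 6 to 15 | 11 to 12 points (Cohort 2's dose expanded); 9 down to 4 (Cohort 1's) |
| Final analysis, last entry + 36 months | −0.2 to 1.4 points |
| Onset through day 84 only | at most about 0.3 points, which is simulation noise |

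If all risk falls within the first 84 days, the gap is zero.

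**Chance error.** Across the 36 settings the SD of the difference is 14 to 22 points. A single term is higher on the unexpanded dose in 50–76% of replicates and lower in 22–50%. An observed 2/6 has a Clopper-Pearson 95% interval of 4% to 78%.

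**The case against.** The strongest reply is that planned outputs already reveal the imbalance.

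- Exposure duration is tabulated for the SAF, PAS and FAS (SAP Appendix A, Tables 3.1.1.2 to 3.1.1.5). For a patient still on treatment it is essentially TEAE follow-up. In the worked case median exposure is 9.0 vs 5.2 months. It is a weak guide only when treatment is short (4.0 vs 3.5 months at a 4-month median).
- First and last enrolment dates are not confined to the overall column.
- The AE listings give start days, so with about 6 patients events by day 84 can be counted by hand.
- Time to onset is summarised for neutropenia and febrile neutropenia (SAP 10.2.4.1.2), and neutropenia leads the reactions in Protocol Table 7.

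All of this stands. It refutes a reading in which the reader is blind to unequal follow-up. It does not supply a TEAE percentage on equal footing, and the onset summaries cover two terms only.

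A second reply is that nothing planned depends on the contrast. The primary estimand pools the PAS, no tests are planned, and the expansion dose is chosen beforehand with DSMC recommendations guided by a common 35-day window. This also stands. A reader might infer that dose selection or the primary safety conclusion is biased; the documents do not support that.

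A third is redaction. SAP 5.2 breaks off, and only the enrolled-set tables name dose group explicitly. The finding is therefore limited to the visible text. If the PAS and SAF columns turn out to be cohorts, the contrast differs from the one modelled.

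**Conclusion.** The point holds as a minor one. At the C3D28 cut, crude TEAE percentages by dose group are expected to run higher for the unexpanded dose on late-accruing terms, by about 2 to 16 points at equal constant risk and less if risk is front-loaded. That range rests on assumed accrual, treatment duration, event rate and group split; it is not an estimate for this trial.

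The shift is in expectation only. A reader might take it to mean that the unexpanded dose will look worse in the report. With about 6 patients it often will not, because chance error exceeds the shift. Early-onset events, the 35-day DSMC reviews, the choice of expansion dose and the pooled PAS estimand are little affected, and the final analysis all but closes the gap.

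The case for acting is that the shift is foreseeable and removable from data already collected, and that SAP 6.2.3 already intends to describe follow-up maturity for safety. Separately, the estimand runs to the last 90-day visit, so percentages at this cut are interim values. That is normal, but the tables should say so.

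**What to change.** 1. In SAP 10.2.4.1.2, for the primary completion analysis, add for the PAS (and the SAF if wanted) a by-dose-group summary of TEAEs, Grade 3 or higher TEAEs, serious TEAEs and AESIs with onset or worsening from Day 1 through Day 84. Keep all participants in the denominator. Footnote the number with under 84 days of TEAE follow-up at the cut-off. Also footnote events that fall in the window only because a missing or partial onset date was imputed; SAP 10.2.1.3 sets a wholly missing onset to Day 1, so an undated late event would otherwise be counted as early.
2. In SAP 6.2.3, add median TEAE follow-up by dose group: first dose to the earliest of last dose + 90 days, end of TEAE collection, or cut-off.
3. Footnote the crude percentages at this cut as interim relative to the primary estimand. If dose columns are compared descriptively, refer to the day-84 table for late-accruing terms.

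The cost is a few extra programmed tables and one row; the crude tables stay. The day-84 window says nothing about later events, and with about 6 patients it remains imprecise.
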